1. INTRODUCTION

Breathlessness is a common reason for people to consult their healthcare professional (HCP) and can have various causes, including psychological factors. However, in most cases, the origin is pulmonary or cardiovascular. HCPs (e.g., general practitioner, practice assistant, practice nurse, clinician) often find it challenging to distinguish between different causes of breathlessness because distinguishing dyspnea causes in primary care is hard with limited diagnostics. Referral to secondary care may be needed if the cause is unclear or initial treatment fails. A Danish study conducted in a hospital dyspnea clinic found that the initial diagnosis made by the HCP was correct in only 31% of patients referred to cardiologists and in 58% of patients referred to pulmonologists. This discrepancy may lead to delays in correct diagnosis and proper treatment. Moreover, there is considerable overlap between both causes of breathlessness, which requires an integrated approach. The Danish study revealed that heart failure was the sole cause in 17% of cases, pulmonary disease in 35%, and combined heart and lung disease in 14% of 284 patients examined.

In a large study of a middle-aged Swedish population, the primary conditions contributing to breathlessness included respiratory disease, anxiety or depression, obesity, and heart disease or chest pain, with a high level of overlap (Figure 1). ³ Notably, 66% of the examined participants (n=1097) had two or more of these conditions.

[figure not shown]

Figure 1. Overlap of underlying contributing conditions to breathlessness

Investigations into patients presenting with breathlessness in general practice often lack a structured approach and clear guidance. A study using a large UK electronic medical database, which analysed adults presenting with breathlessness, revealed that haemoglobin testing was

conducted in 69% of patients, though anaemia was diagnosed in only 5% of cases. Moreover, after two years, most patients (57%) still had no relevant diagnosis recorded.⁴

A Dutch study assessing the efficiency of integrated care provided by both a cardiologist and a pulmonologist found that patients received diagnoses nearly one month earlier than through consultations with non-integrated specialists. ¹

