4.3 Sample size determination

The sample size was determined to reliably demonstrate that there is a difference in the number of days between presentation with breathlessness in the clinic and diagnosis of a disease or disorder causing this breathlessness between usual care and the BiaB intervention.

For stepped-wedge clustered designs, the sample size is a combination of the number of clusters, the number of sequences, the number of time periods and the number of individuals per cluster period.⁷ Research shows that the best method of estimating the required sample size for a

stepped-wedge design is to simulate the power based on the method of analysis proposed including time in the chosen model.^{8,9} Therefore, for this study a sensitivity analysis has been performed using a desired power of 80% for the test of the intervention, with a type I (two-tailed) error rate of 0.05. The analysis was performed using the US National Institute for Health Stepped-wedge Group-Randomized Trials (SWGRT) Calculator software.¹⁰

The following assumptions were considered:

- The expected cluster autocorrelation (between two consecutive periods at the cluster level) was estimated 0.8, as healthcare professionals (HCPs) will use standard protocols or guidelines which are not expected to change between consecutive (6 week) periods within the study period.
- The intra class correlation was set to 0.03 based on previous data.¹¹
- The expected individual autocorrelation (between two consecutive periods at the level of the patient) was estimated 0.8, as HCPs will use standard protocols or guidelines which are not expected to change between consecutive (6 week) periods within the study period.
- The decay-structure for over-time correlations is Block-exchangeable.
- The churn rate was set to 0.0, as the study consists of one visit for data collection and data essential for the primary objective can be retrieved from HCPs.
- The number of patients per sequence (3 practices) is 60.
- Variation in cluster size is not taken into account as 60 patients will be included per cluster for analyses.
- The expected distribution of the primary outcome, dichotomous was set to 0.3.
- There are 6 time periods (including usual care and BiaB intervention period).

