- The hypothesized intervention effect as a difference of time to diagnosis from presentation with breathlessness between usual care and BiaB intervention is 0.2 (20% reduction of time to diagnosis (in days) based on data from the BiaB pilot study, assumed differences between countries the assumption that the average time to diagnosis in usual care will be 70 days and the assumption that a reduction of 14 days is assumed clinically relevant). The 70 day period is chosen after discussions with the scientific advisory board,

including general practitioners, pulmonologists and cardiologist from the Netherlands, Spain and the United Kingdom, because after an extensive literature search, no timed pathway could be found. This 70 days is based on knowledge of access times to several diagnostic tests and clinical experience.

Calculations showed that with 60 patients per cluster (20 patients per site, 5 sequences, 3 countries) and 3 sites per sequence per country we have sufficient power to detect an absolute difference in effect of 0.055 and a standardized detectable difference of 0.114 (i.e. 5.5-11.4%, respectively).

When assuming the outcome as a continuous effect of 0.2 with a variance of 0.1, we would have sufficient power to detect an absolute difference in effect of 0.0362 and a standardized detectable difference of 0.1144 (i.e 3.6 and 11.4%).

In terms of feasibility, Okkes et al. show an average of 2 to 3 patients present with breathlessness per primary care facility in the Netherlands monthly,¹² and other research shows the prevalence of breathlessness is even higher in Spain.¹³ This means the determined study period is sufficient to find 20 patients to participate per site during the study.

5. BiaB procedures

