6.1.1 Primary study endpoint

The primary endpoint is days between presentation with or consultation for breathlessness and a diagnosis causing the breathlessness (usual care group versus BiaB intervention group).

Required variables:

- Date of presentation with breathlessness,
- Date of first consultation for breathlessness,
- Date of diagnosis, and
- Type of diagnosis.

Strategy: Data will be retrieved during patient consultation (presentation and consultation for breathlessness) and periodically (up to 12 months, to account for referral waiting times) from healthcare professional (HCP) reporting (date and type of diagnosis). The exact date of presentation with breathlessness, consultation and diagnosis will be recorded. If exact date of presentation is unknown, it will be set to [01/MM/YYYY], where MM is the month where symptoms started. If duration of presentation is >1 month and start date is unknown, it will be set to either [01/01/YYYY] or [01/07/YYYY] (whichever is most accurate). Date of diagnosis is defined as date of recorded diagnosis related to breathlessness by any HCP (either reported by

HCP or noted in referral documentation) or start of treatment related to breathlessness. If multiple diagnoses are recorded, all will be collected, and the first diagnosis is used to determine time to diagnosis. Patients with missing data will be censored. In countries where a preliminary diagnosis is entered int the medical records to make prescription of medication possible before diagnostic tests are performed, the date of diagnosis will be validated by the HCP to ensure final clinical diagnosis date.

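### Section 4.3 does not show power for the 14-day target: 0.2 is used as a risk difference, the variance has no source, and each patient is counted six times

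*Protocol*

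**What the plan says.** Protocol section 6.1.1 defines the outcome in days: "The primary endpoint is days between presentation with or consultation for breathlessness and a diagnosis causing the breathlessness". Only the first diagnosis counts, so each patient gives one time. Section 3 allows one visit per patient, in either the usual care or the BiaB period.

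Section 4.3 aims for a "desired power of 80% for the test of the intervention, with a type I (two-tailed) error rate of 0.05". The clinical target is in days: "the average time to diagnosis in usual care will be 70 days and the assumption that a reduction of 14 days is assumed clinically relevant". But the inputs are on other scales:

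- Outcome: "The expected distribution of the primary outcome, dichotomous was set to 0.3". The event is not named.
- Effect: "0.2 (20% reduction of time to diagnosis (in days) based on data from the BiaB pilot study".
- Correlations: ICC 0.03, cluster autocorrelation 0.8, individual autocorrelation 0.8, block-exchangeable, churn 0.0, six periods, 60 patients per cluster.

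The reported results are a detectable difference of 0.055 (standardised 0.114), read as 5.5-11.4%, and, "When assuming the outcome as a continuous effect of 0.2 with a variance of 0.1", a detectable difference of 0.0362 (standardised 0.1144), read as 3.6 and 11.4%. No power for 14 days is given, and no SD in days.

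**The concern.** A relative cut of 20% in a waiting time is a different quantity from a change of 0.2 in a proportion, and no dichotomous primary endpoint exists in this trial. A standardised difference is a number of SDs and becomes a percentage of 70 days only once an SD is given. Zero churn with an individual autocorrelation describes a cohort measured again in every period, which this trial does not have.

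At stake is the justification for 900 patients and the reading of the result. Someone relying on section 4.3 would think that reductions of about 4 to 11% are detectable, and could take a null result as evidence against effects that the trial may not be able to see.

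**Working it through.** **Model.** Stepped wedge with 5 sequences and 6 periods, fixed period effects, generalised least squares on cluster-period means, total variance 1. With m patients per cluster-period, ICC 0.03 and between-period correlation 0.03 × 0.8 = 0.024:

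- variance of a cluster-period mean = [1 + (m − 1) × 0.03] / m
- covariance between periods = [0.8 + (m − 1) × 0.024] / m if the same patients are measured each time, or 0.024 if each patient is measured once
- detectable difference = (t at 0.975 + t at 0.80) × SE, with df = clusters − 7 (six periods and one treatment effect)

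**Step 1: reproduce the plan.** Take 15 clusters (5 sequences × 3 countries) of 60, with the same 60 in all six periods. The variance is 2.77/60 = 0.0462 and the covariance 2.216/60 = 0.0369. The SE is 0.0358, df = 8, and the multiplier is 2.306 + 0.889 = 3.195.

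- Standardised: 3.195 × 0.0358 = 0.1144 (stated 0.1144).
- Continuous: 0.1144 × √0.1 = 0.0362 (stated 0.0362).
- Dichotomous, 0.3 versus 0.5: mean variance (0.21 + 0.25)/2 = 0.23; 0.1144 × √0.23 = 0.0549 (stated 0.055).
- Other readings of the dichotomous input: 0.3 alone gives 0.0524, 0.3 versus 0.1 gives 0.0443, and 0.3 versus 0.24 (a 20% relative cut) gives 0.0507. None rounds to 0.055.

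So 0.2 appears to have been added to a proportion of 0.3. The match also depends on 900 × 6 = 5,400 observations, where the trial will have 900.

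**Step 2: the continuous variance.** If the unit is a fraction of 70 days, 0.2 × 70 = 14 days and √0.1 × 70 = 22.1 days. The protocol does not state that unit and gives no source for the variance.

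**Step 3: correct the scale only.** In the protocol's own repeated-measures model, power for 14 days is 99% at an SD of 70 days and 93% at 100 days. It falls to 80% at 14/0.1144 = 122 days.

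**Step 4: one observation per patient.** Recruitment is assumed even over the six periods.

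- 45 sites, m = 20/6 = 3.33: variance 0.321, covariance 0.024, SE 0.0977, df 38, multiplier 2.876; detectable 0.281 SD.
- 15 clusters, m = 60/6 = 10: variance 0.127, covariance 0.024, SE 0.1065, df 8, multiplier 3.195; detectable 0.340 SD.

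That is 2.5 to 3.0 times the stated 0.114. Power = F_t[14/(SD × SE) − t at 0.975]. For 45 sites at an SD of 70: 0.2/0.0977 − 2.024 = 0.02, which gives 51%.

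| Assumed SD (days) | Detectable days, 45 sites / 15 clusters | Power for 14 days, 45 sites / 15 clusters |
|---|---|---|
| 22 | 6.2 / 7.5 | >99% / >99% |
| 50 | 14.1 / 17.0 | 80% / 62% |
| 70 | 19.7 / 23.8 | 51% / 34% |
| 100 | 28.1 / 34.0 | 28% / 18% |

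Power of 80% for 14 days needs an SD of at most about 50 days (14/0.281) with 45 sites, or 41 days (14/0.340) with 15 clusters.

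**The case against.** Four points can be made for the plan.

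1. *The continuous version is coherent.* If its unit is a fraction of 70 days, 0.2 is 14 days with an SD of 22 days, and power exceeds 99% even with one observation per patient. This stands. A reader might call that version wrong in scale, but the text does not require it. Its faults are an unsourced variance, the 11.4% reading and the repeated counting.

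2. *Scale alone does little harm.* This also stands: step 3 leaves 99% power at an SD of 70 days. The loss in step 4 comes from counting each patient once.

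3. *The trial has not been shown to be underpowered.* Correct. A reader might infer that a 14-day effect has about even odds of being missed. That holds only at an SD near 70 days with 45 sites, and the protocol gives no SD in days. It also states detectable differences and makes no explicit power claim for 14 days, so the accurate criticism is that power is not demonstrated.

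4. *The introduction's UK figure does not settle it.* It reports that "after two years, most patients (57%) still had no relevant diagnosis recorded", and a reader might cut the expected number of diagnoses accordingly. That does not fit the plan's own premise: exponential times with mean 70 days leave only exp(−365/70) = 0.5% undiagnosed at 12 months. The UK figure also comes from a records database at two years, whereas section 6.1.1 uses reports from healthcare professionals for up to 12 months and also counts start of treatment.

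Detail could be left to a statistical analysis plan, but section 4.3 is the protocol's own case for 900 patients, and the figures printed there are the ones in question.

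**Conclusion.** The concern holds in this form: none of the detectable differences in section 4.3 applies to days to diagnosis measured once per patient, so power for 14 days is not demonstrated. The misreading of 0.114 as 11.4% and the undefined dichotomous outcome are plain on the page. That 0.2 was run as 0.3 versus 0.5 is an inference from reproducing 0.055. The sixfold counting is supported by reproducing 0.1144 and 0.0362.

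Corrected, the standardised detectable difference is 0.28 to 0.34, depending on whether the cluster is the site or the group of three sites. Whether 14 days is within reach depends on an SD that the protocol does not give: comfortably at 22 days, borderline or short at 50, not at 70 or above. These results keep the protocol's ICC and cluster autocorrelation and assume even recruitment and a comparison of means.

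**What to change.** In section 4.3:

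- Delete the dichotomous 0.3 input and both percentage readings (5.5-11.4%, and 3.6 and 11.4%).
- Recalculate in days or as time-to-event, for 14 of 70 days, with one observation per patient. Remove the zero churn and the individual autocorrelation, and say whether the cluster is the site or the three-site group.
- State the SD in days and its source. Use the 122-patient pilot if it holds this; section 1 reports no spread of times, so otherwise declare the SD as an assumption.
- Tabulate the detectable difference and the power for 14 days over a range of SDs, for example 22 to 100 days.

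The cost is a recalculation and revised wording. Enrolment is unchanged; the stated figure becomes less favourable.

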2. OBJECTIVES

Primary objective:

• To demonstrate whether BiaB use shortens time to diagnosis as compared to usual care without BiaB use.

Secondary objectives:

- To demonstrate whether BiaB use increases the number of new diagnoses of COPD and/or heart disease as compared to usual care without BiaB use
- To demonstrate usability and efficiency of BiaB.

3. Study design

A prospective stepped-wedge study design will be used for this study (Figure 4). In every country, participating sites will be assigned randomly to one of the five sequences (3 sites per sequence) for timing of the intervention start. Each sequence starts with a usual care period (6 weeks or a multiple of 6) which will be followed by a transition period of 4 weeks prior to the BiaB intervention

period (6 weeks or a multiple of 6). During the transition period the healthcare professionals (HCPs) at the site will be instructed about the start date of the BiaB intervention and they will receive training for the use of BiaB. The study duration for sites is 40 weeks in total. The maximum study duration for patients is one visit followed by a maximum of 4 quarterly questionnaires (1 year).

There will be 15 sites per country, amounting to a total of 45 sites for The Netherlands, Spain and Portugal. Per site 20 patients will be included for analysis during the 40-week study period, amounting to 300 patients per country and 900 in total for 3 countries. Per site the number of patients seen in the usual care period and BiaB intervention period will differ, but at the end of the study this study design should yield a ratio of 1:1 (usual care or BiaB intervention).

[figure not shown]

Figure 42. BiaB stepped-wedge study design. All sites (15 per participating country) will be randomly assigned to one of the sequences with set periods of usual care, transition, and BiaB intervention. In total 20 patients will be included per site, amounting to 300 patients per country and 900 patients in total.

Data will be collected (i) during the visit, and (ii) using questionnaires sent to patients and HCPs. Electronic medical data will be extracted from the participating GP practices before, during and at the end of the study. Data collected during the usual care period and, if possible, retrospective data will be used as a control to examine endpoints.

4. Study population

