6.1 Study parameters/endpoints

For all study endpoints, the analysed population will include patients from usual care and the BiaB intervention period.

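### The quoted rate of 2 to 3 breathless patients per practice per month does not support the statement that the study period suffices for 20 participants per site

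*Protocol*

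**What the plan says.** Protocol section 4.3 (Sample size determination) ends with a feasibility argument. It cites "an average of 2 to 3 patients present with breathlessness per primary care facility in the Netherlands monthly", adds that the prevalence of breathlessness is higher still in Spain, and concludes: "This means the determined study period is sufficient to find 20 patients to participate per site during the study".

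Section 3 (Study design) sets the target: "Per site 20 patients will be included for analysis during the 40-week study period", which over 45 sites makes 900. On time, it says "The study duration for sites is 40 weeks in total", with usual care and BiaB periods in multiples of 6 weeks and, between them, usual care "which will be followed by a transition period of 4 weeks prior to the BiaB intervention" period. Section 6.1 says that for all endpoints "the analysed population will include patients from usual care and the BiaB intervention period".

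The power calculation in section 4.3 takes the target as certain: "Variation in cluster size is not taken into account as 60 patients will be included per cluster for analyses". A cluster here is three practices of 20.

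**The concern.** The feasibility sentence moves from patients who present to patients who take part with no step between. Section 4.2 excludes acute worsening of known disease without suspected comorbidity and patients who cannot understand and sign the consent form. Section 9.2 makes participation voluntary. No eligible or consenting fraction is stated. The time available is also shorter than 40 weeks if the transition does not contribute analysed patients.

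The sentence carries weight. It is the only support in the protocol for 20 per site, and so for 60 per cluster and 900 overall. The reason given for ignoring variation in cluster size is that exactly 60 will be included. If the quoted rate does not deliver 20, the stated detectable difference is conditional on a sample that the protocol has not shown it can reach, and the equal-size assumption loses its basis. Section 6.5 adds that patients who leave are not replaced.

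**Working it through.** **Inputs.** Rate 2 to 3 presenters per facility per month (section 4.3, Netherlands). Site duration 40 weeks and transition 4 weeks (section 3). Analysed patients from usual care and BiaB (section 6.1). Target 20 per site and 45 sites (section 3). ICC 0.03, cluster autocorrelation 0.8, individual autocorrelation 0.8, churn 0, 60 per cluster, 6 periods, 80% power, two-sided 0.05, variance 0.1 in the continuous version (section 4.3).

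**Step 1. The plan's own detectable difference.** Take 15 clusters (3 per sequence, 5 sequences), each with m = 60 patients measured in all 6 periods. The variance of a cluster-period mean, in SD² units, is (1 + (m − 1) × 0.03)/m. The covariance between periods is 0.03 × 0.8 + (1 − 0.03) × 0.8/m. Generalised least squares with 6 period effects and one intervention effect gives a standard error of 0.0358. With t quantiles on 8 df (15 clusters minus 7 fixed effects; the df is inferred), the multiplier is 3.195:

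3.195 × 0.0358 = 0.1144 SD, and 0.1144 × √0.1 = 0.0362.

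Both match section 4.3.

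**Step 2. Recruiting time.** 40 − 4 = 36 weeks, which agrees with six 6-week periods. 36 × 7/30.44 = 8.28 months.

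**Step 3. Presenters per site and participation needed.** Presenters = rate × months; participation needed = 20/presenters.

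| Rate per month | Presenters, 36 weeks | Needed for 20 | Presenters, all 40 weeks (9.20 months) | Needed for 20 |
|---|---|---|---|---|
| 2 | 16.6 | 121% | 18.4 | 109% |
| 2.5 | 20.7 | 97% | 23.0 | 87% |
| 3 | 24.8 | 81% | 27.6 | 72% |

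The low end reaches exactly 20 only if all 40 weeks count, transition included, as ten 4-week months, and every presenter enrols. At 2 a month over 36 weeks with every presenter enrolled, 45 sites would give 45 × 16.56 ≈ 745 patients.

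**Step 4. Illustrative yield.** The protocol gives no participation fraction, so these are assumptions that show a range. At 80% the yield is 13.2, 16.6 or 19.9 per site at 2, 2.5 or 3 a month. At 60% it is 9.9, 12.4 or 14.9.

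**Step 5. Detectable difference at smaller sizes, equal cluster sizes.** The first result column repeats step 1 with m = 3 × patients per site. The second takes one observation per patient: 45 practices, n/6 patients per practice-period, between-period covariance 0.03 × 0.8 only, 38 df (45 − 7), multiplier 2.876.

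| Per site | Total | Plan's own model | One observation per patient |
|---|---|---|---|
| 20 | 900 | 0.114 SD | 0.28 SD |
| 15 | 675 | 0.121 SD | 0.32 SD |
| 10 | 450 | 0.133 SD | 0.38 SD |

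At 16.6 per site the plan's own model gives about 0.119 SD. The difference between the two columns comes from the choice of model, which is a separate point. The effect of accrual is read down a column, not across.

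**The case against.** Four points on the other side carry weight.

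- **The rate is Dutch.** Thirty of the 45 sites are elsewhere, and section 4.3 says that prevalence is higher in Spain. This stands as a limit on the shortfall, but does not rescue the sentence. No consultation rate is given for Spain, the cited reference concerns, by its title, dyspnoea among patients with COPD, nothing is given for Portugal, and the 15 Dutch sites are also set at 20 each.
- **The eligible pool may be wider.** Section 4.1 also admits patients with known disease and residual or increasing breathlessness. If the Dutch rate leaves them out, the percentages above are too high. The protocol does not say.
- **The top of the range works.** At 3 a month, 81% participation gives 20. This stands: the target is not impossible.
- **The power loss is modest.** On the plan's own model, halving enrolment moves the detectable difference only from 0.114 to 0.133 SD.

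A reader might infer three stronger things that the documents do not support.

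- **That the sample will fall well below 900.** This needs a participation fraction, and the protocol gives none.
- **That the trial is therefore underpowered.** The hypothesised effect is 0.2/√0.1 = 0.63 SD in the continuous version and about 0.42 to 0.44 SD in the binary one. The 0.38 SD at 10 per site lies below both. Only a stricter reading (one observation per patient, 15 clusters, 8 df) takes power for the binary effect under 80%: 78% at an assumed 70% of low-end presenters and 65% at 50%.
- **That fast sites will fill before using BiaB and spoil the 1:1 ratio.** Filling in week 29, with a 61:39 split, needs 3 a month and every presenter enrolled. At 81% participation, 20 is reached at about week 36 and the split is 50:50.

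**Conclusion.** The point holds as a failed inference. At the one rate quoted, 36 recruiting weeks yield 16.6 to 24.8 presenters per site, and 20 participants needs 81% to 121% of them before exclusions and refusals. At the bottom of the range the target cannot be met even with universal enrolment; at the middle it needs nearly everyone.

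This rests on two assumptions: that transition weeks contribute no analysed patients, and that the quoted rate describes the eligible pool. Dropping the first still leaves 72% to 109%. The second cannot be settled from the protocol. The 20 per site, and the fixed 60 and 900 built on it, are therefore unsupported by the figures offered. The correction is worth making because the protocol uses that size as certain, and as its reason for ignoring cluster-size variation.

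**What to change.** 1. Replace the feasibility sentence in section 4.3 with the expected number enrolled per site over 36 weeks, by country, from a stated presentation rate, eligible fraction and consenting fraction. Say whether the rate includes patients with known disease and residual breathlessness. Where a country has no rate, label the figure as an assumption and give a range.
2. Remove the argument that cluster-size variation can be ignored because exactly 60 per cluster will be included.
3. Restate the detectable difference at, for example, 10, 15 and 20 per site with unequal cluster-period sizes. The equal-size values in the working are a starting point; unequal sizes will generally make them somewhat larger.

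The cost is protocol wording and one recalculation. The downside is that the stated size and detectable difference become less favourable. No change to the design or to the enrolment rules is needed for this point.
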